9.2.4 Matching

Not applicable

9.2.5 Baseline Period

Not applicable

9.2.6 Study Follow-up

Not applicable

9.3 Variables

Individual site characteristics:

- Primary care/ secondary care/ speciality
- Number of patients with each relevant study indication seen per year
- Number of patients with each relevant study indication who are prescribed LMT during the conduct of the study
- Lipid guidelines followed at site (and if Yes then which ones)
- Previous/current experience of lipid-lowering RCT conduct

Subject level:

- Referral to study physician (eg referred from specialist or GP, and date referred)
- Demographics (gender, age at enrolment, ethnicity if permitted to record)
- Relevant medical history (CV events including dates, known risk factors [smoking, family history], diabetic/hypertension/renal/rheumatoid arthritis status, vascular bed involvement)
- Participation in a clinical study within previous 12 months
- Height/weight/BP/waist circumference
- Lipid profile (including fasting status) (total cholesterol, LDL, HDL, non-HDL, triglycerides, Lp(a), apo B100, apo A1), HbA1c, plasma glucose (including fasting status)
- LMT (type, dose, dose frequency, duration of prescription) at enrolment; in 12 months prior to enrolment, up to and including enrolment date
- History of intolerance to higher doses than currently, or to other statins
- Reason for prescription if non-ASCVD (eg diabetic, CKD, subject request)
- Other concomitant therapies of interest (antihypertensives, antidiabetics, antiplatelets, acetylsalicylic acid)

9.3.1 Exposure Assessment

Not applicable.

9.3.2 Outcome Assessment

Primary Outcome Measure:

LDL-C measurement most recent to enrolment (within previous 14 months)

Secondary Outcome Measures:

- Lipid levels (total cholesterol, non-HDL-C, HDL, triglycerides, Lp(a), apo B100, apo A1) most recent to enrolment (within previous 14 months)
- Use of LMT (type, dose, frequency) including combination therapy, in 12 months prior to enrolment, up to and including enrolment date
- Clinical characteristics at time of enrolment as assessed in relation to:
 - FH status (diagnosed/ not diagnosed)
 - CV history (see [Appendix B](#) for a list of diagnoses/events)
 - Diabetic status (diabetic/not diabetic; Type 1 or Type II)
 - CKD status (stage, if applicable)
 - CV Risk scores

Exploratory Outcome Measure:

PAM 13 score

9.3.3 Covariate Assessment

Not applicable

9.3.4 Validity and Reliability

Study variables stated in this protocol are objective, and relevant to the question under study. Variables are parameters which are routinely measured as part of clinical management of patients considered or suspected to be at elevated risk of CV event.

9.4 Data Sources

Data will be provided by study site staff, utilising subject medical notes to abstract information in order to complete eCRFs in the electronic study database ('InForm'), which will be provided by ICTU. Sites participating in the study will be fully trained by ICTU in data entry and use of InForm and eCRFs.

9.5 Study Size

The primary outcome measure for the study allows estimation of the percentage of study subjects with LDL-C level above 2016 Joint ESC Guideline-recommended levels. The planned sample size for the study is approximately 6000 subjects across up to 18 countries; the number of subjects enrolled per country will vary according to size of country population and is not anticipated to be fewer than 200 subjects per country.

The sample size is expected to enable precise estimates of the primary outcome measure to be obtained for each participating country.

Table 2 shows the expected precision of the primary outcome measure for subgroups of the full study population, assuming that 50% of subjects achieve the guidelines-recommended LDL-C levels (50% chosen as this results in the widest confidence interval). Sample sizes of 70-150 represent the potential size of cohorts of primary prevention or secondary prevention subjects within a country, while sample sizes of 200-300 represent the potential size of country cohorts.

Table 2. Estimated Precision of Primary Outcome Measure For a Range of Sample Sizes

Sample size	½ width of 95% CI
70	11.7
100	9.8
130	8.6
150	8.0
200	6.9
250	6.2
300	5.7

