- Relevant medical history (CV events including dates, known risk factors [smoking, family history], diabetic/hypertension/renal/rheumatoid arthritis status, vascular bed involvement)
- Participation in a clinical study within previous 12 months
- Height/weight/BP/waist circumference
- Lipid profile (including fasting status) (total cholesterol, LDL, HDL, non-HDL, triglycerides, Lp(a), apo B100, apo A1), HbA1c, plasma glucose (including fasting status)
- LMT (type, dose, dose frequency, duration of prescription) at enrolment; in 12 months prior to enrolment, up to and including enrolment date
- History of intolerance to higher statin doses than currently prescribed, or to other statins
- Reason for prescription if non-ASCVD (eg diabetic, CKD, subject request)
- Other concomitant therapies of interest (antihypertensives, antidiabetics, antiplatelets, acetylsalicylic acid)
- Study Sample Size

The primary outcome measure for the study allows estimation of the percentage of study subjects with LDL-C level above 2016 Joint ESC Guideline-recommended levels (Piepoli 2016). The planned sample size for the study is approximately 6000 subjects across up to 18 countries; the number of subjects enrolled per country will vary according to size of country population and is not anticipated to be fewer than 200 subjects per country.

The sample size is expected to enable precise estimates of the primary outcome measure to be obtained for each participating country. Table 1 shows the expected precision of the primary outcome measure for subgroups of the full study population, assuming that 50% of subjects achieve the guidelines-recommended LDL-C levels (50% chosen as this results in the widest confidence interval). Sample sizes of 70-150 represent the potential size of cohorts of primary prevention or secondary prevention subjects within a country, while sample sizes of 200-300 represent the potential size of country cohorts.

Table 1. Estimated Precision of Primary Outcome Measure For a Range of Sample Sizes

Sample size	½ width of 95% CI
70	11.7
100	9.8
130	8.6
150	8.0
200	6.9
250	6.2
300	5.7

- Data Analysis

Primary analysis is descriptive: To estimate the proportion of subjects having LDL-C above the 2016 Joint ESC Guideline-recommended targets. Specifically, to estimate the proportion separately for subjects with and without established ASCVD.

Other analyses:

- Proportion of subjects with relevant clinical characteristics (ASCVD components, FH, diabetes, CKD)

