9.2.2 Selection and Number of Sites

Site selection:

- Will be carried out according to normal feasibility and selection processes
- Will evaluate both primary and secondary care sites:
- At least 25% of sites will be primary care
- Secondary care sites will be selected proportionately according to speciality, to enable enrolment of a study population enriched for PVD and IS subjects
- Will require sites to demonstrate the ability to provide adequate study data ie, demographics and CV history, at least one LDL within the pre-specified window, and the previous/current LMT regimen

Selection is based on interest in participation as a study site, and willingness and ability to meet the criteria above, and to comply with the protocol and data entry conventions.

It is expected that approximately 160 sites will be selected, across approximately 18 EU countries.

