9.7.2.4 Analysis of the Primary, Secondary and Exploratory Outcome Measures

9.7.2.4.1 Analysis of Primary Outcome Measure

Summaries displaying the frequency and percentage with 95% confidence interval will be presented for LDL-C within or above the 2016 Joint ESC Guideline-recommended targets. Subjects will be presented overall and split into subgroups with and without established ASCVD.

Subjects included in the secondary prevention cohort will fulfil the following:

- Documented history of MI or revascularisation (peripheral, carotid or coronary), ischaemic stroke, or symptomatic PVD, as defined in [Appendix B](#), except for patients diagnosed with familial hypercholesterolaemia (FH).
- Subjects without a history of MI or revascularisation are eligible if they have DOCUMENTED angiographic evidence of atherosclerosis defined as $\geq 30\%$ stenosis in at least one coronary artery using either standard coronary angiography or CT coronary angiography.

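### Tables 1 and 2 compute precision as if subjects were independent, although enrolment is clustered in about 160 sites, so the stated country-level precision is too favourable

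*Protocol*

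**What the plan says.** Section 9.5 sets the size: "The planned sample size for the study is approximately 6000 subjects across up to 18 countries". Enrolment varies with country population and "is not anticipated to be fewer than 200 subjects per country". The purpose follows: "The sample size is expected to enable precise estimates of the primary outcome measure to be obtained for each participating country". The abstract repeats this, and section 7.3 says much the same.

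The figures behind the claim are in Table 2, headed "½ width of 95% CI" and identical to Table 1, of which the abstract says: "Table 1 shows the expected precision of the primary outcome measure for subgroups of the full study population". They are derived "assuming that 50% of subjects achieve the guidelines-recommended LDL-C levels (50% chosen as this results in the widest confidence interval". Rows of 70 to 150 stand for primary or secondary prevention cohorts within a country, and rows of 200 to 300 for whole countries.

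On sampling, section 9.2.2 states: "It is expected that approximately 160 sites will be selected, across approximately 18 EU countries". Sites are chosen by care level and speciality, and on interest and ability to supply data. Sections 9.7.2.3.1 and 9.9.1.2 describe inviting eligible patients in order of attendance, up to a site cap.

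For the primary outcome, section 9.7.2.4.1 says: "Summaries displaying the frequency and percentage with 95% confidence interval will be presented for LDL-C within or above" the guideline targets. It names no interval method. No design effect, ICC or cluster allowance appears in the study size, analysis or limitations sections.

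**The concern.** A table that depends only on n and p treats a country's 200 subjects as 200 independent observations. Here they come in groups from a handful of clinics, and patients of one clinic share prescribers, local policy and case mix.

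The protocol itself gives grounds to expect this to matter. Section 9.3 records care level, speciality, lipid guideline followed and lipid-trial experience for each site. Section 9.7.2.4.2 plans to show target attainment by site characteristics. Section 9.9.2 says regional access policy will affect which patients are treated.

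Country-level precision is the stated reason for the sample size, country stratification is the planned subgroup analysis (section 9.7.2.5.1), and section 7 presents cross-country comparison as a contribution of the study. If country estimates are less certain than the table says, chance differences between a few sites could be taken for differences between countries.

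**Working it through.** **Inputs from the protocol.** N about 6000, up to 18 countries, minimum 200 per country, p = 0.50, 95% two-sided interval (section 9.5); about 160 sites (section 9.2.2).

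**Input assumed.** ICC of 0.01 to 0.10. The protocol gives none.

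**Step 1: reproduce the table.** Half-width = 100 × 1.96 × sqrt(0.25/n).

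| n | Computed | Stated |
|---|---|---|
| 70 | 11.71 | 11.7 |
| 100 | 9.80 | 9.8 |
| 130 | 8.60 | 8.6 |
| 150 | 8.00 | 8.0 |
| 200 | 6.93 | 6.9 |
| 250 | 6.20 | 6.2 |
| 300 | 5.66 | 5.7 |

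All seven rows match, so the table carries a design effect of exactly 1.

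**Step 2: cluster size.** Mean subjects per site: 6000/160 = 37.5. Mean sites per country: 160/18 = 8.9. Together these imply 6000/18 = 333 subjects per country, so a country of 200 must have either fewer sites or smaller ones. Both cases are shown:

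- Average-sized sites: 200/37.5 = 5.3 sites.
- Average number of sites: 200/8.9 = 22.5 subjects per site.

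**Step 3: design effect.** DE = 1 + (m − 1) × ICC, and the half-width is multiplied by sqrt(DE). For n = 200 (stated 6.9):

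| Assumed ICC | DE, m = 37.5 | Half-width | DE, m = 22.5 | Half-width |
|---|---|---|---|---|
| 0.01 | 1.365 | 8.1 | 1.215 | 7.6 |
| 0.02 | 1.73 | 9.1 | 1.43 | 8.3 |
| 0.05 | 2.825 | 11.6 | 2.075 | 10.0 |
| 0.10 | 4.65 | 14.9 | 3.15 | 12.3 |

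With m = 37.5 the effective sample size 200/DE is 147, 116, 71 and 43. At ICC 0.05 a country of 200 therefore has about the precision that the table gives to n = 70.

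For n = 300 at 37.5 per site (8 sites, stated 5.7), the half-widths are 6.6, 7.4, 9.5 and 12.2.

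For a prevention cohort of 100 (stated 9.8), assume that half of each site belongs to it, so m = 18.75. The half-widths are 10.6, 11.4, 13.5 and 16.3.

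**Step 4: overall estimate.** At N = 6000 the half-width is 1.3 points for independent subjects and 1.3 × sqrt(2.825), about 2.1 points, at ICC 0.05 with m = 37.5.

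**Step 5: coverage, only if reported intervals are computed as in the table.** Coverage = 2Φ(1.96/sqrt(DE)) − 1. With m = 37.5 this is about 91%, 86%, 76% and 64% at ICC 0.01, 0.02, 0.05 and 0.10.

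Unequal site sizes, and t quantiles for so few sites, would widen the intervals further. An analysis stratified by site type could recover some precision.

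**The case against.** Much of the case for leaving the table alone has force.

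- **The arithmetic is right.** A reader might infer that the table is miscalculated. It is not; the fault lies in the assumption of independence.
- **The p = 50% remark is true.** A reader might take it as a claim that the table is a worst case overall. It says only that 50% gives the widest interval over p, which is correct, and it makes no claim about other sources of error.
- **The primary objective is EU-wide.** It is reported overall and by ASCVD status, and that estimate stays precise. Country results are supportive, section 9.7.2.1 shows them only where numbers allow, and no hypothesis or numeric precision target is at risk.
- **The interval method is unnamed.** A reader might infer that the reported intervals will undercover. The protocol does not say how they will be computed, and an analysis plan may specify a method that allows for clustering. Undercoverage is therefore conditional.
- **The size is not in the documents.** The ICC is assumed, site sizes per country are unknown, and the even split behind the prevention-cohort figures is a simplification, since section 9.1 uses site selection to obtain the prevention mix. Some between-site variation is planned through care level and speciality and need not all count as sampling error. Sites are also chosen purposively, so neither interval has a strict design-based meaning.

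These points limit size and severity. They do not restore the table: the protocol itself prints the figures and rests its country-level claim on them. Uncertainty about the ICC calls for a stated range, not an implicit zero.

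**Conclusion.** The stated precision for countries and for prevention cohorts within countries is too favourable for any positive within-site correlation. The direction is firm and the protocol makes such correlation plausible. The size is illustrative: at n = 200 the stated 6.9 points becomes anything from 7.6 (ICC 0.01, about 9 sites) to 14.9 (ICC 0.10, about 5 sites) over the assumptions shown.

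The documents do not support going further, to say that the table is wrongly calculated, that the EU estimate is imprecise or that the reported intervals will necessarily undercover. The point should be fixed because the sample-size justification rests on it, but it does not undermine the primary analysis.

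**What to change.** - Restate Tables 1 and 2 with the design effect 1 + (m − 1) × ICC, giving the assumed ICC range, the subjects per site and the sites per country.
- Amend the country-level precision statements in the abstract, section 7.3 and section 9.5 to agree with the restated figures.
- State that country-level intervals treat site as the cluster, so that they agree with the restated tables. The exact method can be left to the SAP.

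The cost is two tables and a few sentences, with no extra subjects. The downside is that the stated intervals become wider.

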9.6 Data Management

Data are abstracted by site staff from subject notes into InForm, the electronic database provided by ICTU. ICTU will provide protocol-specific training to all site staff delegated to abstract subject data. An eCRF Completion Guideline is provided.

The Amgen and ICTU representative(s) and regulatory authority inspectors are responsible for contacting and visiting the Investigator for the purpose of inspecting the facilities and, upon request, inspecting the various records of the clinical study (eg, eCRFs and other pertinent data) provided that subject confidentiality is respected. This may also take place remotely by ICTU, as specified by the monitoring plan.

The Clinical Monitor or designee is responsible for verifying the eCRFs at regular intervals throughout the study to verify adherence to the protocol completeness, accuracy, and consistency of the data; and adherence to local regulations on the conduct of research. The Clinical Monitor, or designee is to have access to subject medical records and other study-related records needed to verify the entries on the eCRFs in accordance with the local laws and regulations.

The Investigator agrees to cooperate with the Clinical Monitor, or designee to ensure that any problems detected in the course of these monitoring visits, including delays in completing eCRFs, are resolved.

In accordance with the sponsor's audit plans, this study may be selected for audit by representatives from Amgen's Global Compliance Auditing function (or designees). Review of study-related records will occur to evaluate the study conduct and compliance with the protocol, and applicable regulatory requirements.

Data capture for this study is planned to be electronic, with the exception of reporting of safety events which are to be recorded on a paper form and submitted via fax directly to Amgen (see [Section 11.2](#)):

- All source documentation supporting entries into the eCRFs must be maintained and available upon request.
- Updates to eCRFs will be automatically documented through the software's "audit trail".
- To ensure the quality of clinical data across all subjects and sites, a central clinical data management review is performed at regular intervals on subject data received at ICTU. During this review, subject data is checked for consistency, omissions, and any apparent discrepancies. To resolve any questions arising from the clinical data management review process, data queries and/or site notifications are created in InForm for site resolution and closed by the ICTU monitor.
- Only the Principal Investigator may sign the Investigator Sign Off page for this study. This signature indicates that the Investigator inspected or reviewed the data on the eCRF, the data queries and site notifications, and agrees with the content.

9.6.1 Obtaining Data Files

N/A

9.6.2 Linking Data Files

N/A

9.6.3 Review and Verification of Data Quality

Automatic edit checks within InForm and further manual review by ICTU help to ensure quality and completeness of the data. Data queries are sent to site electronically by ICTU for clarification and resolution of discrepancies.

9.7 Data Analysis

9.7.1 Planned Analyses

9.7.1.1 Interim Analysis

An Interim Analysis may be conducted by Q1 2018 if required for Congress abstract submission.

9.7.1.2 Primary Analysis

The primary analysis will be conducted after completion of enrolment.

9.7.2 Planned Method of Analysis

9.7.2.1 General Considerations

All summaries of the data will be descriptive in nature. No imputation of missing data is planned. A sensitivity analysis to explore the effect of influential subgroups (eg country, clinical characteristics) on the primary outcome measure may be conducted, if appropriate.

Subject demographics, baseline characteristics and PRO scores will be summarised. For categorical variables the frequency and percentage, with 95% confidence interval, will be given.

Summary statistics for continuous variables will include the number of subjects, mean, median, standard deviation or standard error, 25th percentile (Q1), 75th percentile (Q3), minimum, and maximum.

Outcome measures may be presented by country and/or by study site type and/or by subject clinical characteristics, if sample size permits meaningful analysis.

Outcome measures may also be presented by different levels (eg, quartiles) of risk measures (eg REACH, SCORE, QRISK2).

Exploratory analysis will be conducted to identify which characteristics may be associated with subjects being in target, and which may be associated with subjects failing to achieve the LDL-C target.

9.7.2.2 Missing or Incomplete Data and Lost to Follow-up

Missing/incomplete data is a possibility on this study, but is not expected to be significant: Subjects are likely to be followed regularly by their physicians and the variables collected in the eCRF are those captured as part of routine care of this patient population. The feasibility process is intended to identify sites which can provide key inclusion/exclusion data for the study, including key analysis variables (LDL-C, LMT).

No imputation of missing data is planned.

9.7.2.3 Descriptive Analysis

9.7.2.3.1 Description of Study Enrolment

All eligible patients at each study site will be invited by the Investigator to provide informed consent to be enrolled into the study, in chronological order of presenting for a routine visit.

9.7.2.3.2 Description of Subject Characteristics

Subjects are adult patients who have been prescribed lipid-modifying therapy as part of routine treatment at primary and secondary care centres in Europe, and who provide informed consent to participate in the study.

Inclusion criteria have been written to be as inclusive as possible of this population.

9.7.2.4 Analysis of the Primary, Secondary and Exploratory Outcome Measures

9.7.2.4.1 Analysis of Primary Outcome Measure

Summaries displaying the frequency and percentage with 95% confidence interval will be presented for LDL-C within or above the 2016 Joint ESC Guideline-recommended targets. Subjects will be presented overall and split into subgroups with and without established ASCVD.

Subjects included in the secondary prevention cohort will fulfil the following:

- Documented history of MI or revascularisation (peripheral, carotid or coronary), ischaemic stroke, or symptomatic PVD, as defined in [Appendix B](#), except for patients diagnosed with familial hypercholesterolaemia (FH).
- Subjects without a history of MI or revascularisation are eligible if they have DOCUMENTED angiographic evidence of atherosclerosis defined as $\geq 30\%$ stenosis in at least one coronary artery using either standard coronary angiography or CT coronary angiography.

9.7.2.4.2 Analysis of Secondary Outcome Measures

Summaries displaying frequency and percentage, with 95% confidence intervals, will be presented for clinical characteristics (ASCVD components, FH, diabetes, CKD) and for subjects receiving maximally tolerated dose of statins. Also, summaries will be presented for subjects receiving maximally tolerated dose of statin and subjects receiving high, moderate or low intensity statin where LDL-C is above guideline stipulated levels.

Summary statistics displaying the number of subjects, mean, median, standard deviation or standard error, 25th percentile (Q1), 75th percentile (Q3), minimum, and maximum will be presented for lipid levels (total cholesterol, LDL-C, HDL-C, non-HDL-C,

triglycerides, Lp(a), apo B100, apo A1) and for CV risk scores (REACH, SCORE and QRISK2).

Summaries displaying frequency and percentage, with 95% confidence intervals, will be presented for use of lipid lowering therapies (subdivided by type, dose, frequency).

To further investigate predictive factors for subjects not achieving target LDL levels, the proportion (frequency, percentage and 95% confidence intervals) of subjects achieving target LDL levels will be presented by subgroups; demographics, clinical characteristics, site characteristics, country or region.

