therapy offered a further 0.5 mmol/L reduction in LDL- C cholesterol than treatment with low or moderate intensity, indicating even greater predicted benefits than those observed when low or moderate intensity statin therapy was compared to placebo. More recently, clinical trials such as ASCOT, CARDS, JUPITER and HOPE 3 ([Sever 2005](#), [Colhoun 2004](#), [Ridker 2016](#), [Yusuf 2016](#)) have extended the evidence base for the benefit of statin use to populations which are at high risk of vascular disease by virtue of the presence of hypertension, diabetes, elevated C-reactive protein (CRP) or global (ie, multifactorial) risk. As such there is now compelling evidence in favour of regarding 0.7% as the lower risk threshold at which treatment is indicated in the primary prevention setting. Despite these compelling data there remains an apparent lack of appreciation of the benefits of lipid lowering therapies in such patients.

In recognition of the need for appropriate treatment of patients at elevated risk of experiencing a CV event, expert bodies at national and local levels (eg EAS/ESC, national bodies such as NICE in the UK) issue guidelines on classification and clinical management of these patients. However, beyond the EUROASPIRE surveys ([Kotseva et al 2015, 2016](#)) which included patients with recent myocardial infarction (MI), there is little published data describing EU-wide lipid profiles & treatment patterns in patients routinely prescribed LMT, in both primary and secondary care settings. This study is expected to contribute new information on the patterns of treatment in primary and secondary care within the same geographical region as well as cross-country comparisons of lipid modifying therapy utilisation, which to date have not been reliably quantified. It is expected that these results will estimate the gap between guidelines and clinical practice, in turn helping to inform public health initiatives across Europe; by identifying potential shortfalls in treatment the study will contribute data that could be used in the development of policies towards rectifying suboptimal treatment.

Study Rationale

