7.3 Statistical Inference (Hypothesis)

No formal hypothesis will be tested in this observational study. The aim of the study is to describe the management of patients receiving lipid-modifying therapy. The sample size is expected to enable sufficiently precise estimates of the primary outcome measures to be obtained for each participating country.

8. Research Question and Objectives

Research Question: How are EU patients requiring lipid-modifying therapy routinely managed?

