9.9.1.3 Confounding

N/A

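### The predictive-factor tables are crude subgroup proportions with confounding marked N/A, although site selection links site type to prevention status and disease mix

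*Protocol*

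**What the plan says.** The protocol fixes both the aim and the method in Section 9.7.2.4.2. The sentence begins "To further investigate predictive factors for subjects not achieving target LDL levels, the proportion (frequency, percentage and 95% confidence intervals" and goes on to say that the proportion at target will be tabulated by demographics, clinical characteristics, site characteristics, and country or region. Section 9.7.2.1 adds, without a method, "Exploratory analysis will be conducted to identify which characteristics may be associated with subjects being in target". It makes all summaries descriptive, and it allows, but does not require, breakdowns by country, site type and clinical characteristics singly or together.

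The heading "9.9.1.3 Confounding" is followed only by N/A. Section 9.3.3, on covariates, reads not applicable.

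On sampling, Section 9.1 relies on the choice of primary-care or secondary-care sites and on site caps to reach the wanted prevention mix (at least half primary prevention). It also seeks MI, PVD and ischaemic stroke patients in the ratio 1:2:2 through specialist sites. Section 9.2.2 sets at least 25% of sites in primary care and picks secondary-care sites by speciality. Section 9.9.2 says that access policies will affect the clinical characteristics of patients in different locations.

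On countries, Section 9.7.2.5.1 repeats the planned analysis by country, and Section 9.7.2.4.1 splits the primary result by ASCVD status. The Abstract promises "cross-country comparisons of lipid modifying therapy utilisation, which to date have not been reliably quantified".

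**The concern.** Calling a factor predictive invites the reader to see it as a source of poor control in its own right. Site type cannot be read that way from a crude table here. The design uses site type as the lever for prevention status and for vascular and stroke enrichment, and the guideline target may be met at different rates in those groups. If so, primary-care and secondary-care sites would differ in the table even if they managed the same kind of patient equally well.

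The N/A entry makes this worse, because it tells the analyst and the reader that there is nothing to allow for. It also sits badly with the protocol's own remark that case mix varies by location. The protocol hopes that its results will show shortfalls in treatment and inform policy, so an artefact of site selection could be taken for one.

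**Working it through.** **1. The plan's own figure.** Table 2 in Section 9.5 is built "assuming that 50% of subjects achieve the guidelines-recommended LDL-C levels (50% chosen as this results in the widest confidence interval". The formula is 1.96 × √(0.5 × 0.5 / n). For n = 70, 100, 130, 150, 200, 250 and 300 it gives 11.71, 9.80, 8.60, 8.00, 6.93, 6.20 and 5.66 points. All seven rows agree with the table.

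**2. Layout.** Section 9.5: "The planned sample size for the study is approximately 6000 subjects across up to 18 countries". Section 9.2.2 expects about 160 sites.
- Subjects per site: 6000/160 = 37.5
- Sites per country: 160/18 = 8.9; subjects per country: 6000/18 = 333
- At the 25% minimum: 0.25 × 160 = 40 primary-care sites and 120 secondary-care sites. With equal site sizes (an assumption), that is 40 × 37.5 = 1500 and 120 × 37.5 = 4500 subjects.

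**3. Does the mix differ by site type?** Let a be the primary-prevention share at primary-care sites. For 50% primary prevention overall, secondary-care sites need (0.5 − 0.25a)/0.75.
- a = 70%: 43.3%
- a = 80%: 40.0%
- a = 90%: 36.7%
- a = 100%: 33.3%

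The values of a are assumed. Across this range the mix differs by site type.

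**4. Size of the artefact.** Suppose that attainment depends on prevention status only, with no site-type effect. The crude gap is then (a − b) × (p₁ − p₂), where a and b are the primary-prevention shares in primary and secondary care, and p₁ and p₂ are attainment in primary and secondary prevention. The documents give none of these four inputs, so a range is shown.
- Low: (0.70 − 0.40) × (0.55 − 0.45) = 3 points
- Middle: (0.80 − 0.40) × (0.60 − 0.40) = 8 points
- High: (0.90 − 0.30) × (0.60 − 0.30) = 18 points
- Equal attainment, p₁ = p₂: 0 points

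The middle case fits the 50% aim at the 25% minimum: 0.25 × 0.80 + 0.75 × 0.40 = 0.50. The low and high cases fit it if one third of subjects come from primary care, which the minimum permits: 0.70/3 + 0.40 × 2/3 = 0.50 and 0.90/3 + 0.30 × 2/3 = 0.50. If attainment is higher in secondary prevention, the sign reverses.

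**5. How it would look.** With 1500 and 4500 subjects, the 95% half-width of the site-type difference is 1.96 × √(0.25/1500 + 0.25/4500) = 2.9 points. The interval would exclude zero with probability about 0.77, 0.98 and 1.00 for artefacts of 4, 6 and 8 points. These figures ignore clustering within sites, which would lower them.

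**6. Country.** The same formula applied to an overall country table gives (0.70 − 0.50) × 0.10 = 2 points up to (0.70 − 0.30) × 0.30 = 12 points. In the planned tables by country and ASCVD status this component is 0. What remains is site type, the PVD and stroke mix and other case mix, for which the documents give no figures. For two countries of 333 the half-width of a difference is 7.6 points, so an artefact of this size stands out less than one between site types.

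**The case against.** The strongest reply is that the study is descriptive. Section 7.3 states "No formal hypothesis will be tested in this observational study", and a proportion by subgroup is correct as a description. The association analysis in Section 9.7.2.1 has no stated method, so an analysis plan that is not shown could specify a model or a cross-classification. This stands in part: the absence of a regression model is not the finding. But the predictive label, the tabular method and the N/A are all stated in the protocol, and the joint breakdowns that it allows are optional.

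A reader might infer more than the documents support:

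- *That the design ties country to prevention status.* It does not. The 25% and 50% shares are set for the study as a whole, and no section links country to either. The country mix is left uncontrolled, and the stated reason for variation by location is access policy.
- *That country results rest only on one-way proportions.* Sections 9.7.2.4.1 and 9.7.2.5.1 together give the primary proportion by ASCVD status within country, and Section 9.5 considers cohorts of 70 to 150 for that purpose.
- *That country rankings of LDL-C control are promised.* The Abstract speaks of comparing the use of lipid-modifying therapy.
- *That primary-care sites are known to supply mainly primary prevention.* Section 9.1 says only that site selection is meant to help reach the mix, so any single gap is an assumed case.

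**Conclusion.** The point holds for contrasts by site type, and more weakly for contrasts by country. The protocol fixes crude subgroup proportions as its way to find predictive factors and declares confounding not applicable, while its own sampling links site type and speciality to prevention status and disease mix. The possible artefact between site types is about 3 to 18 points, and 0 if attainment is equal in the two prevention groups. This range rests on assumed attainment and mix, and on prevention status being the only source of difference.

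The primary estimate, with and without ASCVD, is not touched by this point, nor is the precision in Table 2. The correction is worth making before analysis but does not threaten the main result.

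**What to change.** 1. In Section 9.7.2.4.2, show site-type and other predictive-factor results within prevention status, or standardised to a common mix of prevention status and ASCVD type, beside the crude proportions. A model with prevention status, ASCVD type, age, sex, site type and country, allowing for clustering by site, would serve equally well.
2. Do not adjust country or site-type contrasts for LMT intensity. That is part of the practice that the study sets out to describe. It may also be unrecorded at the LDL-C date: Section 9.3.2 covers LMT for 12 months before enrolment but accepts an LDL-C up to 14 months old.
3. In Section 9.9.1.3, replace N/A with a statement that crude contrasts are confounded by site selection and case mix.
4. Call the results associations, not predictors.

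The main variables are already on the list in Section 9.3. The cost is a few extra tables, and some loss of subjects with incomplete covariates in the standardised or modelled results, since no imputation is planned.
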